2.5.3 Handling of intercurrent events

Not Applicable.

2.5.4 Handling of missing values not related to intercurrent event

Missing data will not be replaced.

2.5.5 Sensitivity analyses

Not Applicable.

2.6 Analysis supporting secondary objectives

2.6.1 Secondary endpoint(s)

Secondary objective [1] is to describe the long-term efficacy of ligelizumab as measured by the tolerance of an allergen food protein during an open-label OFC at scheduled timepoints.

To satisfy the above secondary objectives the following endpoint will be taken into consideration:

Proportion of participants tolerating a single dose of \geq 600 mg of peanut protein without dose-limiting symptoms during an open label OFC at scheduled timepoints. This analysis will be based on FAS.

Secondary objective [2] is to assess the safety and tolerability of ligelizumab in all participants who administered study treatment at home by self-administration or parent/caregiver.

To satisfy the above secondary objectives the following endpoint will be taken into consideration:

Overall incidence rates of treatment emergent-AEs and SAEs will be analysis based on SAF-1.

Secondary objective [3] is to assess the long-term impact of ligelizumab on the health-related quality of life (HRQoL) of patients with food allergy.

To satisfy the above secondary objectives the following endpoint will be taken into consideration:

Summaries of total scores in the FAQLQ, FAIM, and SF-36v2 by age group and responder (participants and/or parent/caregiver) at scheduled timepoints.

This analysis will be based on FAS and latest available value at each visit will be used for summary.

Note: SF-36v2 completed by adults only.

For all efficacy endpoints, if missing Week 52-OFC assessments, Week 156-OFC assessments performed within 380 days (inclusive) after first extension dose date will be considered as Week 52-OFC assessments.

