- Participants who meet the definition of MR by DBPCFC at EoT of the core study and transition from the core study at EOFu will perform an OL-OFC at Screening/Day 1:
 - If the participants still meet the definition of MR by OL-OFC on Day 1, the off-treatment period will be continued until Week 52.
 - If the participants are no longer MR by OL-OFC on Day 1, the study treatment will be started (same dose as in the core study) after at least 24 h from completion of the OL-OFC on Day 1. If participants become MR again at a later timepoint, no interruption of treatment is commenced. The study treatment will continue until the EoT of the extension study (Week 156).
- NOTE: The Investigator is able to check the level of desensitization by SPT at Week 24 (scheduled time point) and can decide to conduct ad hoc OL-OFC in case of positive (or

shift from prior assessment) SPT. The same (SPT followed by OL-OFC) is allowed in case of suspected allergic event during the off-treatment period. The results of the ad hoc OL-OFC may lead to the resumption of study treatment (same dose as in the core study) after at least 24 h from completion of the OL-OFC and treatment will continue until the EoT of the extension study (Week 156).

• Participants who did not meet the definition of MR by DBPCFC at EoT of the core study and transition from the core study at EOFu will not perform an OL-OFC at Screening/Day 1. Study treatment will be started (same dose as in the core study) until week 52.

Second year:

[figure not shown]
- For participants who have been off-treatment in the first year until Week 52 (i.e., MR participants since Day 1):
 - 1. If the participants still meet the definition of MR by OL-OFC at Week 52, the off-treatment period will continue up to Week 104 of the extension study.
 - 2. If the participants are no longer MR by OL-OFC at Week 52, the study treatment will be re-started (same dose as in the core study) after at least 24 h from completion of the OL-OFC. If the participants become MR again at a later timepoint, no interruption of treatment is commenced. The study treatment will continue until the EoT of the extension study (Week 156).

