9.3.2 Statistical model, hypothesis, and method of analysis

There is no pre-specified hypothesis for the primary endpoints, and no inferential analysis will be done for the primary endpoints.

Summary statistics will be provided.

Summaries will include: 1) the number and percentages of participants with at least one event (incidence rates); and 2) exposure-adjusted occurrence rates (the number of events per participant year of exposure). The following treatment-emergent AE summaries will be provided for the Safety Set 1 (SAF-1), presented by dose and cumulative duration of exposure:

- Overall, by primary system organ class and preferred term,
- Overall, by primary Standardized MedDRA Query (SMQ) and preferred term,
- Overall, by primary system organ class, preferred term and maximum severity,
- Suspected drug-related AEs by primary system organ class and preferred term,
- SAEs by primary system organ class and preferred term,
- AEs leading to permanent discontinuation of study-drug by primary system organ class and preferred term,
- Adverse events of special interest (AESI).

Other tables will be generated to summarize safety data for participants in SAF-1 who restarted study treatment after a protocol mandated interruption period (> 16weeks). Details will be provided in the SAP.

Summaries will be performed as well for non-TEAEs for participants who did not receive any study treatment doses during the extension study (SAF-2).

Separate summaries will be provided for study treatment-related adverse events, death, serious adverse events, and other significant adverse events leading to discontinuation. If a participant reported more than one AE with the same preferred term, the AE with the greatest severity will be presented. If a participant reported more than one AE within the same primary system organ class, the participant will be counted only once with the greatest severity at the system organ class level, where applicable.

Other safety analyses (laboratory data, vital signs, ECG) are described in Section 9.4.2.

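### The SAP rule that moves an early Week 156 challenge to Week 52 has no start date for participants who never receive an extension dose

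*SAP*

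**What the plan says.** - **The rule.** SAP 2.6.1 opens it with "For all efficacy endpoints, if missing Week 52-OFC assessments" and continues: "Week 156-OFC assessments performed within 380 days (inclusive) after first extension dose date will be considered as Week 52-OFC assessments". It sets an upper limit and an anchor but no lower limit. It follows the quality-of-life endpoint and addresses efficacy endpoints generally, so I read it as also covering the questionnaires completed around that challenge.
- **The columns.** SAP 2.6.2 reports the proportion tolerating at least 600 mg at Weeks 52, 104 and 156. In protocol Table 1-4 these are Days 364, 728 and 1092, counted from Screening/Day 1.
- **Participants with no dose in year 1.** Protocol 4.1.2.1 says of core-study MR participants: "If the participants still meet the definition of MR by OL-OFC on Day 1, the off-treatment period will be continued until Week 52".
- **Participants with no dose at all.** Protocol 9.3.2 plans a separate summary for "participants who did not receive any study treatment doses during the extension study (SAF-2", and SAP 2.8 still refers to that set.
- **The setting.** SAP section 1 states that the study was terminated early. SAP 2.6.1 bases the challenge endpoint on the FAS.

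**The concern.** The re-labelling rule appears intended to stop a challenge done at early termination, but recorded under the final visit name, from being reported as a three-year result. Its window starts at a date that one foreseeable group does not have. For that group the condition cannot be met, so the record keeps its Week 156 label however early it was taken.

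The group is not a random one. Being MR on Day 1 means no dose-limiting symptom at any step of the challenge, including the maximum. Protocol Table 10-8 has steps above 600 mg, so these participants met the 600 mg criterion on Day 1. At stake is whether two reported proportions, Week 52 and Week 156, describe the times they name. Off-drug durability is also of direct interest, since the protocol lists guidance on potential discontinuation among the study's aims.

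**Working it through.** **Inputs.** 380-day limit and first-dose anchor: SAP 2.6.1. Visit days 168 (Week 24), 364, 728 and 1092: protocol Table 1-4. Off-treatment and restart rules: protocol 4.1.2.1. Day 300 below is my illustration.

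**1. The plan's figures.** 52 × 7 = 364 and 156 × 7 = 1092 match the schedule. 380 − 364 = 16. The visible SAP does not explain the 16 days, so I take 380 as given.

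**2. Last study day that can be re-labelled.** With the first extension dose on study day d, this is d + 380.
- Dosed on Day 1: 1 + 380 = Day 381 (381 / 7 = Week 54.4).
- First dose on Day 2, the earliest for someone no longer MR on Day 1 (24 h wait): 2 + 380 = Day 382.
- Never dosed: d does not exist, so there is no limit to compare with.

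**3. Two participants, same study day.** Both lack a Week 52 challenge, and both have a terminal challenge on Day 300 recorded as Week 156.

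| | Dosed on Day 1 | Never dosed |
|---|---|---|
| Days since first extension dose | 300 − 1 = 299 | undefined |
| Within 380 days? | yes | cannot be evaluated |
| Column | Week 52 | Week 156 |
| Distance from that column's scheduled day | 364 − 300 = 64 days | 1092 − 300 = 792 days |

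**4. With a Day 1 date for the never-dosed participant.** 300 − 1 = 299 ≤ 380, so the record moves to Week 52 and both are treated alike.

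**5. Should the Day 1 anchor apply to everyone?** Take an MR participant off drug since Day 1 who restarts after an ad hoc challenge at Week 24. The first dose is on Day 168 + 1 = 169 at the earliest, and the window then closes on 169 + 380 = Day 549 (Week 78.4). Day 549 is 549 − 364 = 185 days from Week 52 and 1092 − 549 = 543 days from Week 156. The visible rule chooses only between those two columns. A Day 1 anchor would close the window on Day 381 and leave challenges on Days 382 to 549 under Week 156, which is the worse placement.

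**6. Direction.** If affected participants exist, they leave the Week 52 count and enter the Week 156 count. Having passed the full challenge on Day 1, they are likely, though not certain, to be responders later. Early termination probably leaves few genuine Week 156 records, so a few misplaced ones could weigh heavily there. SAP section 3 expects about 200 participants in all.

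**The case against.** The strongest objection is that the effect depends on text that is not visible. The FAS definition (protocol 9.1, SAP 2.2) does not appear in the public documents, and the general definitions in SAP 2.1.1 are redacted. If the FAS requires a dose, never-dosed participants are in no efficacy column. If SAP 2.1.1 supplies a substitute start date, the gap is already closed. Neither can be excluded, so the point has to be conditional. Inclusion is plausible, because protocol 6.3.1 allocates all eligible participants through IRT and MR participants remain under challenge follow-up, but it is not shown.

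Three further limits stand. The rule acts only when the Week 52 challenge is missing, so a never-dosed participant who completed it is unaffected. That off-drug MR participants had a terminal challenge recorded as Week 156 is inferred from the rule; protocol 7.5 treats participants at early termination as having discontinued treatment, and 7.1 ends further planned challenges for such participants. Finally, the SAP announces purely descriptive analyses.

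A reader might also infer that the dose anchor misplaces everyone who starts or restarts drug late. The documents do not support that.
- Under "If the participants are no longer MR by OL-OFC on Day 1, the study treatment will be started" the anchor can move by as little as one day.
- Participants restarted because of their Week 52 challenge have that challenge, so the rule is not triggered.
- Participants dosed from Day 1 and interrupted at Week 52 or 104 keep a Day 1 anchor.
- This leaves MR participants off drug since Day 1 who restart before Week 52 and then lack a Week 52 challenge. In the Week 24 example, Week 52 is the nearer of the two columns that the rule offers.

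**Conclusion.** The gap is real but narrow, and minor. Read literally, SAP 2.6.1 places first-year terminal challenges, and the questionnaires tied to them, under Week 156 for never-dosed MR participants, while participants dosed on Day 1 and assessed on the same study day go to Week 52. This rests on three conditions: never-dosed participants are in the FAS, the redacted definitions give them no substitute date, and their Week 52 challenge is missing.

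The likely direction is a higher Week 156 proportion and fewer responders at Week 52. A reader might want to state the bias in percentage points. The documents give neither the share of participants never dosed, nor how many of them lack a Week 52 challenge, nor any response rate, so no such figure can be derived. A reader might also blame the anchor for every early result reported under Week 156. That goes too far: a terminal challenge taken after the window closes keeps that label in dosed participants too.

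**What to change.** In SAP 2.6.1, directly after the reference to the first extension dose date, add an alternative start: the extension Screening/Day 1 date, for FAS participants with no extension dose. Leave the 380-day limit unchanged, and keep the dose anchor for everyone who was dosed, for the reason in step 5 of the working.

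The cost is one phrase in the SAP and one line in the derivation program. No new data are needed, and no dosed participant's result moves. If the unpublished FAS definition already excludes never-dosed participants, or the general definitions already give them a start date, a cross-reference at this point in 2.6.1 is enough.

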1.2 Study objectives, endpoints and estimands

Due to the early termination of the study, purely descriptive analyses will be performed for primary, secondary endpoints, and part of exploratory endpoints.

Table 1-1 Objectives and related endpoints

*	
Objective(s)	Endpoint(s)
Primary objective(s)	Endpoint(s) for primary objective(s)
To evaluate the long-term safety and tolerability of ligelizumab in participants with food allergy	Overall incidence and exposure-adjusted occurrence rates of treatment-emergent AEs and SAEs
Secondary objective(s)	Endpoint(s) for secondary objective(s)
To describe the long-term efficacy of ligelizumab as measured by the tolerance of an allergen food protein during an open-label OFC at scheduled timepoints	 Proportion of participants tolerating a single dose of ≥ 600 mg of peanut protein without dose-limiting symptoms during an open label OFC at scheduled timepoints
 To assess the safety and tolerability of ligelizumab in all participants who administered study treatment at home by self-administration or parent/caregiver 	 Overall incidence and exposure-adjusted occurrence rates of treatment emergent-AEs and SAEs
 To assess the long-term impact of ligelizumab on the health-related quality of life (HRQoL) of patients with food allergy 	 Summaries of total scores in the FAQLQ, FAIM, and SF-36v2 by age and responder (participants and/or parent/caregiver) at scheduled timepoints
Exploratory objective(s)	Endpoint(s) for exploratory objective(s)

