2.6.2 Statistical method of analysis

The analysis of proportion of participants tolerating a single dose of \geq 600 mg of peanut protein without dose-limiting symptoms during an open label OFC at scheduled timepoints will be summarized with number and percentage of responders at Week 52, Week 104 and Week 156 by treatment group and overall.

To evaluate for all participants who administered study treatment at home by self-administration or parent/caregiver under the second secondary endpoints analysis for overall incidence of treatment-emergent adverse events (TEAEs) and serious adverse events (TESAEs) will be summarized as per Section 2.5.2.

Summaries for change from baseline in FAQLQ, SF-36v2 and FAIM domain and total scores will also be provided by age group and responder (participants and/or parent/caregiver) at scheduled timepoints (Refer Section 2.12).

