2.6.4 Handling of missing values not related to intercurrent event

Missing data will not be imputed.

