2.6.5 Sensitivity analyses

Not Applicable.

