2.14 Interim analysis

Not applicable.

3 Sample size calculation

The expectation is that approximately 200 participants from the study CQGE01G12301 will enroll in this extension study.

4 Change to protocol specified analyses

5 Appendix

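### SAP 2.6.1 lets an early end-of-treatment food challenge stand in for a missing Week 52 result with an upper day limit but no visible lower one, and SAP 2.6.2 does not show how many results were reassigned

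*SAP*

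**What the plan says.** The endpoint is the proportion of participants who tolerate a single dose of at least 600 mg of peanut protein at an open-label OFC at scheduled timepoints (SAP 2.6.1). The last sentence of that section, written for every efficacy endpoint, deals with a missing Week 52 challenge: "Week 156-OFC assessments performed within 380 days (inclusive) after first extension dose date will be considered as Week 52-OFC assessments".

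Under SAP 2.6.2 the proportion "will be summarized with number and percentage of responders at Week 52, Week 104 and Week 156 by treatment group and overall". No row separates scheduled Week 52 challenges from those moved there by the rule, and SAP 2.6.5 plans no sensitivity analysis.

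The protocol's Table 1-4 puts the Week 52 OFC on Day 364 and the Week 156 OFC on Day 1092. Protocol 4.1.2.1 identifies Week 156 as the end of treatment. Protocol 1.3 asks participants who permanently stop treatment to complete the end-of-treatment visit as soon as possible. Protocol 7.5 has participants seen as soon as possible on early termination and handled as treatment discontinuations. SAP Section 1 records that the sponsor terminated the study early, and SAP 1.2 says that "purely descriptive analyses will be performed for primary, secondary endpoints".

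**The concern.** The 380-day limit shows that closeness to one year mattered to the authors, yet it works on one side only. A challenge soon after the first extension dose meets the condition as fully as one on Day 360.

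Readers of the Week 52 row will take it as tolerance after about a year, since the objective is long-term efficacy at scheduled timepoints. Followed as written, the rule would place an end-of-treatment OFC brought forward by weeks or months in that row, and the table would not reveal it. In a purely descriptive analysis the row label carries most of the meaning of the number, so what is at stake is how one proportion is read.

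**Working it through.** The 380-day figure is a chosen cut-off with no derivation in either document, so there is nothing to reproduce. The check is day and dose arithmetic.

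1. **Nominal days (Table 1-4).** Week 52: 52 × 7 = 364. Week 156: 156 × 7 = 1092. Both match the schedule.

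2. **What a Week 156 OFC inside the limit must be.** 1092 − 380 = 712. It takes place at least 712 days before its nominal day, so it is an end-of-treatment challenge brought forward.

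3. **Late side.** For a participant first dosed on Day 1, 380 − 364 = about 16 days past nominal.

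4. **Early side.** The only bound in the sentence is the first dose.
   - OFC at Week 24 (Day 168): 364 − 168 = 196 days early, and it counts.
   - OFC at Week 4 (Day 28): 364 − 28 = 336 days early, and it counts.
   - A limit that mirrored the late side would be 364 − 16 = Day 348. Days 1 to 347 lie before it, which is 347/380 = 91% of the admitted days. This is a share of days, not of participants.

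5. **Doses received, for a participant dosed every 4 weeks from Day 1.**
   - Scheduled Week 52: Day 1, Weeks 4 to 48 (12 doses) and Week 52 = 1 + 12 + 1 = 14.
   - OFC at Week 4: 1, or 2 if dosed that day.
   - OFC at Week 24: Day 1 and Weeks 4, 8, 12, 16 and 20 = 6, or 7 if dosed that day.
   - OFC on Day 348: 1 + 12 = 13.

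6. **Effect on the reported percentage.** Let N be the number with a Week 52 result after the rule is applied, k the number of those reassigned, pS the proportion tolerating among scheduled challenges and pE that among reassigned ones. The pooled proportion is ((N − k) × pS + k × pE)/N, so it differs from pS by (k/N) × (pE − pS). Its size cannot exceed k/N. SAP Section 3 states that "The expectation is that approximately 200 participants from the study CQGE01G12301 will enroll in this extension study". If all 200 had a Week 52 result, each reassigned result would move the overall percentage by at most 1/200 = 0.5 points. With fewer results, or within one treatment group, the bound per result is larger. If k = 0 there is no shift. The documents give neither k nor pE − pS.

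**The case against.** **A window may exist in redacted text.** SAP 2.1.1, the general definitions, is blacked out, and the definition of the full analysis set is not visible. A lower limit could be there. This stands as a limit on the finding: it says that the rule and the rest of the readable SAP contain none, and the rule's sentence points to no other window. Even with a window, the number reassigned would not be reported.

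**Early challenges may be rare or absent.** Protocol 7.1 says that participants who stop treatment have no further OFC planned at their remaining visits, and 7.5 handles early termination the same way. Nothing shows that an OFC took place at Week 4 or Week 24, and a cut-off just past one year also fits close-out challenges done near Day 364. This stands, and it is why no size is claimed. It does not repair the rule, which presupposes that some challenges labelled Week 156 happen within 380 days. A reader might infer that any early challenge breached the protocol. The documents do not support that: the reference to remaining visits can be read as excluding the end-of-treatment visit itself, and 7.5 allows additional procedures.

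**Conflict with the missing-data rule.** A reader might infer one, because SAP 2.6.4 says "Missing data will not be imputed". There is none. The rule assigns an observed challenge in the same participant to an analysis visit and creates no value.

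**On-treatment versus off-treatment results.** A reader might infer that reassignment mixes treated with untreated participants. Scheduled Week 52 results already do so by design. For maximum responders (MR) who transition off treatment, Protocol 4.1.2.1 says: "If the participants still meet the definition of MR by OL-OFC on Day 1, the off-treatment period will be continued until Week 52". Protocol 6.2.3 has a dose before the OFC at Week 156 as at Week 52. The concern is timing alone.

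**The clock starts at first dose.** A reader might infer that a late restart pushes the upper limit far past one year. That needs an unlikely chain of events (still MR on Day 1, restart in mid-year, a missed Week 52 OFC, then a later challenge labelled Week 156). For participants never dosed, the rule does not apply and Week 52 stays missing. I do not rest anything on this.

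**Conclusion.** The point holds as a minor one. On the readable text, the reassignment rule has an upper limit of about 16 days past Day 364 and no lower limit other than the first extension dose, and the planned table pools reassigned with scheduled results without a count. If an end-of-treatment OFC was brought forward well before one year and the Week 52 OFC was missing, it would be reported as a Week 52 result.

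A reader might go further and infer that the Week 52 percentage is biased by a material amount or in a known direction. The documents do not support that. The number reassigned and the difference in tolerance are both unknown, and the only firm statement is that the shift cannot exceed k/N. No hypothesis test or error rate is involved. The conclusion assumes that the redacted definitions contain no visit window that already excludes early challenges. If they do, only the missing count remains.

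**What to change.** Preferred: in SAP 2.6.2, show the Week 52 result by treatment group in two rows, one for scheduled Week 52 OFCs and one for reassigned early end-of-treatment OFCs, with the number reassigned and their study-day range.

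Alternative: add a lower day limit to the rule in SAP 2.6.1 and list earlier challenges by study day. Day 348 would mirror the 16-day late allowance. It is a suggestion, not a figure from the documents. If SAP 2.1.1 already sets a window, a cross-reference in 2.6.1 is enough for the limit and only the count needs adding.

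The cost is a sentence or two, or two table rows, and no new data. The downside is a smaller headline Week 52 denominator.
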